Clinical Study Protocol: DEF-315

Study Title:	A Phase III, Open-Label, Multicenter Trial to Evaluate Ejection Fraction, End-Diastolic and End-Systolic Volumes, by Unenhanced and DEFINITY®-enhanced 2D-Echo and Magnetic Resonance Imaging
Study Number:	DEF-315
Study Phase:	Phase 3
Product Name:	DEFINITY®
IND Number:	048626
Indication:	DEFINITY® is indicated to improve the accuracy of left ventricular ejection fraction measurements with echocardiography.
Investigators:	Multicenter
Sponsor:	Lantheus Medical Imaging, Inc.
Sponsor Contact:	[name] [contact]
Medical Monitor:	[name]

	Date
Original Protocol	07 February 2018
Amendment 1	02 May 2018
Amendment 2	12 June 2018
Amendment 3	15 August 2018

Confidentiality Statement

This document is the confidential property of Lantheus Medical Imaging (LMI). No part of it may be transmitted, reproduced, published, or used by other persons without the permission of LMI.

SYNOPSIS

Sponsor: Lantheus Medical Imaging, Inc.
Study Title:
A Phase III, Open-Label, Multicenter Trial to Evaluate Ejection Fraction, End-Diastolic and End-Systolic Volumes, by Unenhanced and DEFINITY®-enhanced 2D-Echo and Magnetic Resonance Imaging
Study Number: DEF-315
Study Phase: Phase 3
Primary Objective(s): The primary objective of this study is to demonstrate improvement in accuracy in left ventricular ejection fraction (LVEF) assessment using DEFINITY® contrast-enhanced over unenhanced echocardiography.
Secondary Objective(s): The secondary objectives of this study are to: 
1. Demonstrate improvement in accuracy in left ventricular ejection fraction (LVEF) assessment using DEFINITY® contrast-enhanced over unenhanced echocardiography in subjects with suboptimal echocardiograms.2. Demonstrate a reduction in inter-reader variability for the assessment of LVEF using DEFINITY® contrast-enhanced versus unenhanced echocardiography.3. Demonstrate a reduction in inter-reader variability for the assessment of end-diastolic/systolic volumes using DEFINITY® contrast-enhanced versus unenhanced echocardiography.4. Demonstrate a reduction in inter-reader variability for the assessment of LVEF using DEFINITY® contrast-enhanced versus unenhanced echocardiography in subjects with suboptimal echocardiograms.5. Demonstrate a reduction in inter-reader variability for the assessment of end-diastolic/systolic volumes using DEFINITY® contrast-enhanced versus unenhanced echocardiography in subjects with suboptimal echocardiograms.

Study Design:

This is a Phase 3, prospective, open-label, multicenter study to evaluate LVEF measurement accuracy and reproducibility of DEFINITY® contrast-enhanced and unenhanced echocardiography as compared with non-contrast cardiac magnetic resonance imaging (CMR) used as the truth standard.

Subjects will be enrolled over approximately 10 months at approximately 10 centers located in the United States. Subjects will be screened based on LVEF measurements obtained via 2D echo with or without contrast or other methods (e.g. CMR, MUGA scan) obtained within 6 months of enrollment (Day 0) to achieve an approximately even distribution within four pre-defined LVEF groups (>50, 41-50, 30-40, <30%). Subjects with optimal and sub-optimal echocardiograms will be enrolled.

Each patient will undergo an unenhanced ultrasound examination and a DEFINITY® contrast-enhanced examination on the same day at Day 0. Subjects will remain at the clinical site for at least 30 minutes of observation after DEFINITY® administration. The site investigator will determine whether an echocardiogram is optimal or sub-optimal based on the unenhanced echocardiogram performed on Day 0.

A non-contrast CMR will be used as the truth standard. CMR studies will be performed within ± 30 days of the echocardiographic assessments at Day 0. Final assignment of each subject to an LVEF group will be determined by CMR.

In addition, a safety follow-up phone call will be conducted at 72 ± 24 hours after DEFINITY® administration.

All echocardiography images will be interpreted by 3 experienced independent blinded readers at a central imaging core laboratory. A single, independent, blinded echocardiologist will read each subject's unenhanced echocardiogram as either optimal or suboptimal. This will be independent of the site investigator determination. All CMR images will be read centrally by a single reader. Echocardiographic imaging data will be compiled, analyzed, and stored without knowledge of the CMR findings.

Study Population:

Approximately one hundred and fifty (150) evaluable subjects will be enrolled at approximately 10 US centers. Subjects who have had a 2D echo with or without contrast or other methods (e.g. CMR, MUGA scan) to evaluate screening LVEF within 6 months prior to enrollment (Day 0) may be enrolled. The study population will consist of males and non-pregnant and non-lactating females 18 years-of-age or older.

Duration of Treatment:

Subjects will receive DEFINITY® treatment once as a part of a single day imaging session.

Study Treatment:

DEFINITY® will be administered as a diluted bolus injection. 1.3 mL of activated DEFINITY® will be diluted with 8.7 mL of preservative-free saline to evenly distribute microspheres. An initial injection of up to 3 mL of diluted DEFINITY® will be administered with subsequent injections of 1 to 2 mL, as needed.

Efficacy Assessments:

The primary endpoint is to demonstrate an improvement in LVEF accuracy from unenhanced imaging to imaging with DEFINITY® contrast enhancement using CMR as the truth standard.

The secondary endpoints are to:

1. Demonstrate improvement in accuracy in left ventricular ejection fraction (LVEF) assessment using DEFINITY® contrast-enhanced over unenhanced echocardiography in subjects with suboptimal echocardiograms.
2. Demonstrate a reduction in inter-reader variability for the assessment of LVEF using DEFINITY® contrast-enhanced versus unenhanced echocardiography.
3. Demonstrate a reduction in inter-reader variability for the assessment of end-diastolic/systolic volumes using DEFINITY® contrast-enhanced versus unenhanced echocardiography.
4. Demonstrate a reduction in inter-reader variability for the assessment of LVEF using DEFINITY® contrast-enhanced versus unenhanced echocardiography in subjects with suboptimal echocardiograms.
5. Demonstrate a reduction in inter-reader variability for the assessment of end-diastolic/systolic volumes using DEFINITY® contrast-enhanced versus unenhanced echocardiography in subjects with suboptimal echocardiograms.

Safety Assessments:

Enrolled subjects will be followed for adverse events (AEs), serious adverse events (SAEs) and changes in concomitant medications from the time the Informed Consent (IC) is signed through 72±24 hours after completion of DEFINITY® administration. All AEs will be recorded on the electronic case report form (eCRF). The National Cancer Institute Common Terminology Criteria for Adverse Events (NCI-CTCAE) version 4.0 will be utilized for Adverse Event (AE) reporting of severity.

Statistical Methods for Primary Objective:

The primary objective of the study is to demonstrate improvement in accuracy in left ventricular ejection fraction (LVEF) assessment using DEFINITY® contrast-enhanced over unenhanced echocardiography, using CMR as the truth standard.

The following analyses will be carried out for each of the three blinded readers. For each subject, the absolute value of the difference of DEFINITY® LVEF minus CMR LVEF will be calculated. Similarly, the absolute value of the difference of unenhanced imaging

LVEF minus CMR LVEF will be calculated for each subject. The primary analysis is to assess the significance of the difference between DEFINITY® and unenhanced echo with respect to the mean “absolute value of the difference vs. CMR”. These means will be compared with a paired t-test at a two-sided 0.05 level of significance. Specifically, the null and alternative hypotheses are:

$$H_0: \mu_D = \mu_U \text{ vs. } H_1: \mu_D \neq \mu_U$$

Where μ_D is the mean of the absolute value of the differences between the DEFINITY®-enhanced echo LVEF and the CMR LVEF. Similarly, μ_U is the mean of the absolute value of the differences between the unenhanced echo LVEF and the CMR LVEF. A sample of size of 150 enrolled subjects has 90% power to reject the null hypothesis in favor of the alternative if the true difference $\mu_D - \mu_U$ is at least 2.75 with a standard deviation of 10 or less and allows for approximately 5% premature withdrawal. If the null hypothesis is rejected in favor of DEFINITY® for at least two of three blinded readers, the primary analysis will be considered a success.

The following are additional analyses to be carried out separately for each blinded reader to achieve the primary objective:

Bias is the mean of the actual (not absolute value) per-subject differences between the imaged LVEF and CMR LVEF. The bias, the two-sided 95% confidence interval of the bias, the precision (standard deviation of the per-subject differences) and the root mean square error (RMSE) will be calculated for DEFINITY®. The RMSE is the square root of the bias-squared + precision-squared and is considered a measure of overall accuracy. These analyses will be repeated for unenhanced echocardiography vs. CMR. It is anticipated that the RMSE will be smaller for DEFINITY®-enhanced LVEF than for unenhanced LVEF.

DEFINITY®-enhanced and unenhanced echocardiography LVEF will each be assessed for measurement accuracy against the reference CMR using Bland-Altman analysis and Deming regression analysis. For the Bland-Altman analysis, a plot of per-subject actual difference between DEFINITY®-enhanced echocardiography and CMR LVEF will be plotted vs. the per-subject sum of the two measurements. Limits of agreement (defined as the mean of the DEFINITY® vs. CMR difference) ± 2 SD will be shown on the plot. Similar analyses will be carried out for the unenhanced echocardiography LVEF again using CMR as the reference standard.

Deming regression plots of LVEF vs. CMR LVEF will be generated for each of DEFINITY®-enhanced and unenhanced echocardiography. Unweighted Deming regression will be employed to estimate the regression slope and intercept with two-sided 95% confidence intervals of each, assuming the measurement error is the same for CMR and each of the echocardiography error techniques.

The intra-class correlation coefficient (ICC) and its two-sided 95% confidence interval will be calculated for DEFINITY®-enhanced echo vs. CMR and for unenhanced echo vs. CMR.

Statistical Methods for Secondary Objectives:

A secondary objective of this study is to demonstrate improvement in accuracy in left ventricular ejection fraction (LVEF) assessment using DEFINITY® contrast-enhanced over unenhanced echocardiography in subjects with suboptimal echocardiograms. For this, the above analyses for the primary objective will be repeated on subjects with suboptimal echocardiograms.

An additional secondary objective is to demonstrate a reduction in inter-reader variability for the assessment of LVEF and End-Diastolic/Systolic volumes using DEFINITY® contrast-enhanced versus unenhanced echocardiography. The inter-observer variability among each pair of readers within each imaging modality will be estimated using an intra-class correlation coefficient (ICC); descriptive comparisons of the ICC between DEFINITY® and unenhanced echocardiography will be carried out. Similar analyses will be conducted for the final secondary objective of assessing inter-reader variability within subjects with suboptimal echocardiograms.

TABLE OF CONTENTS

SYNOPSIS.....	2
LIST OF ABBREVIATIONS AND DEFINITIONS OF TERMS.....	11
1 INTRODUCTION	14
1.1 Background.....	14
2 STUDY OBJECTIVES.....	15
2.1 Primary Objective	15
2.2 Secondary Objectives.....	15
3 INVESTIGATIONAL PLAN	16
3.1 Overall Study Design and Plan.....	16
3.2 Rationale for Study Design.....	17
3.3 Study Duration	18
4 STUDY POPULATION	19
4.1 Inclusion Criteria	19
4.2 Exclusion Criteria	19
5 STUDY TREATMENT(S)	21
5.1 Description of Treatment(s)	21
5.1.1 Investigational Product	21
5.2 Treatments Administered.....	21
5.2.1 Administering Study Drug.....	21
5.3 Selection and Timing of Dose for Each Patient.....	21
5.4 Method of Assigning Subjects to Treatment Groups.....	21
5.5 Blinding.....	22
5.6 Concomitant Therapy.....	22
5.7 Treatment Compliance.....	22
5.8 Packaging and Labeling.....	22
5.9 Storage and Accountability.....	22
5.10 Investigational Product Retention at Study Site	22
6 STUDY PROCEDURES	23
6.1 Screening.....	23
6.2 Informed Consent.....	23
6.3 Medical History	23
6.4 Physical Examination.....	24
6.5 Vital Signs.....	24

6.6	Pregnancy Test.....	24
6.7	Cardiac Magnetic Resonance Imaging	24
6.7.1	Image Acquisition.....	24
6.7.2	Imaging Core Laboratory.....	25
6.8	Echocardiography Imaging Procedures	25
6.8.1	Image Acquisition.....	25
6.8.2	Imaging Core Laboratory.....	26
6.9	Efficacy Assessments.....	26
6.9.1	Primary Efficacy Assessments.....	26
6.9.2	Secondary Efficacy Assessments.....	26
6.10	Adverse Event Assessments	26
6.10.1	Performing Adverse Event Assessments	26
6.10.2	Timing.....	28
6.10.3	Severity	28
6.10.4	Relationship	29
6.10.5	Clinical Significance	29
6.10.6	Serious Adverse Events	29
6.10.6.1	Definition	29
6.10.6.2	Reporting Serious Adverse Events	30
6.11	Removal of Subjects from the Trial or Investigational Product	31
7	QUALITY CONTROL AND ASSURANCE	32

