8.3 Secondary Endpoint(s)

8.3.1 Secondary Efficacy Endpoint(s)

- 8.3.1.1 Improvement in accuracy in left ventricular ejection fraction (LVEF) assessment using DEFINITY® contrast-enhanced over unenhanced echocardiography in subjects with suboptimal echocardiograms

The above primary analyses will be repeated here, but on the subgroup of subjects with suboptimal echocardiograms. There will be no imputation of missing data for this analysis.

- 8.3.1.2 Reduction in inter-reader variability for the assessment of LVEF using DEFINITY® contrast-enhanced versus unenhanced echocardiography

The inter-observer variability among each pair of readers within each imaging modality will be estimated using an intra-class correlation coefficient (ICC). The ICC assesses rating reliability by comparing the variability of different ratings of the same subject with the total variation across all ratings and all subjects. The inter-observer variability in the assessment of LVEF between two readers will be determined by percentage of error. The percentage of error will be calculated using the formula:

Percentage of error = SD between 2 measurements/ mean of the 2 measurements x 100

The mean percentage of error and its 95% confidence interval will be calculated for each pair of readers within each imaging modality.

There will be no imputation of missing data for this analysis.

8.3.1.3 Reduction in inter-reader variability for the assessment of end-diastolic/systolic volumes using DEFINITY® contrast-enhanced versus unenhanced echocardiography

The above analyses used to assess inter-reader variability on LVEF will be carried out, but on end-diastolic/systolic volumes. There will be no imputation of missing data for this analysis.

8.3.1.4 Reduction in inter-reader variability for the assessment of LVEF using DEFINITY® contrast-enhanced versus unenhanced echocardiography in subjects with suboptimal echocardiograms

The above analyses used to assess inter-reader variability on LVEF will be carried out, but on the subgroup of subjects with suboptimal echocardiograms. There will be no imputation of missing data for this analysis.

8.3.1.5 Reduction in inter-reader variability for the assessment of End-Diastolic/Systolic volumes using DEFINITY® contrast-enhanced versus unenhanced echocardiography in subjects with suboptimal echocardiograms

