8.2. Secondary Efficacy Endpoint(s) and Analyses

8.2.1. Improvement in accuracy in LVEF assessment using DEFINITY® contrast-enhanced over unenhanced echocardiography in subjects with suboptimal echocardiograms

The primary endpoint analysis will be repeated in the subset of subjects with suboptimal echocardiograms. This will include all primary analyses described in sections 8.1 and 8.1.1, excluding the supportive analyses at the end of section 8.1. The study is not powered to reject the primary endpoint null hypothesis, so the focus is more on the estimate of $\mu_D - \mu_U$, on Bland-Altman plots and on the Deming regression for each blinded reader. There will be no imputation of missing LVEF data for this analysis.

8.2.2. Reduction in inter-reader variability for the assessment of LVEF using DEFINITY® contrast-enhanced versus unenhanced echocardiography

The inter-reader variability among each pair of readers within each imaging modality will be estimated using an intra-class correlation (ICC) and its two-sided 95% CI. The ICC assesses rating reliability by comparing the variability of different ratings of the same subject with the total variation across all ratings and all subjects. The inter-observer variability in the assessment of LVEF between two readers will be determined by percentage of error. The percentage of error will be calculated using the following formula:

$$\text{Percentage of error} = (\text{SD between 2 measurements} / \text{mean of the 2 measurements}) \times 100$$

The mean percentage of error and its 95% CI will be calculated for each pair of readers within each imaging modality. The pairwise ICCs and percentages of error differences will be compared descriptively between contrast-enhanced and unenhanced echocardiography.

In addition, specific to only section 8.2.2, there will also be a separate ICC analysis to assess intra-reader variability as approximately 10% of all echo results will be re-read by each reader.

This document is confidential.

8.2.3. Reduction in inter-reader variability for the assessment of end-diastolic/systolic volumes using DEFINITY® contrast-enhanced versus unenhanced echocardiography

The same analysis used to assess inter-reader variability on LVEF (section 8.2.2) will be conducted for end-diastolic/systolic volumes.

8.2.4. Reduction in inter-reader variability for the assessment of LVEF using DEFINITY® contrast-enhanced versus unenhanced echocardiography in subjects with suboptimal echocardiograms

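### Both planned measures of inter-reader variability are relative, so neither by itself shows whether readers disagree by fewer LVEF points or mL with contrast

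*Protocol*

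**What the plan says.** Protocol 2.2 and SAP 3.2 list four secondary objectives (2 to 5) on reduced inter-reader variability: for LVEF and for the volumes, each in all subjects and in those with suboptimal echocardiograms.

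- **Protocol synopsis, statistical methods for secondary objectives.** Only the ICC is named: "The inter-observer variability among each pair of readers within each imaging modality will be estimated using an intra-class correlation coefficient (ICC". It adds that "descriptive comparisons of the ICC between DEFINITY® and unenhanced echocardiography will be carried out".
- **Protocol 8.3.1.2.** The ICC is described as "comparing the variability of different ratings of the same subject with the total variation across all ratings and all subjects". A second measure follows: "The inter-observer variability in the assessment of LVEF between two readers will be determined by percentage of error". Its formula is "Percentage of error = SD between 2 measurements/ mean of the 2 measurements x 100", and "The mean percentage of error and its 95% confidence interval will be calculated for each pair of readers within each imaging modality". Sections 8.3.1.3 to 8.3.1.5 carry the same analyses to the volumes and the suboptimal subgroup.
- **SAP 8.2.2.** Inter-reader variability "will be estimated using an intra-class correlation (ICC) and its two-sided 95% CI". Percentage of error is kept, and both measures are compared descriptively between modalities. SAP 8.2.3 to 8.2.5 extend this as the Protocol does.

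Neither document plans an inter-reader measure in LVEF points or mL. Bland-Altman limits, bias and the SD of differences are planned only for echo against CMR (Protocol 8.2.1, SAP 8.1.1). Neither says what counts as a reduction, or which measure governs if the two disagree.

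**The concern.** The objectives concern how far readers differ on the same images. The ICC answers another question: how large reader differences are relative to the spread of measured values. A higher enhanced ICC shows only that the ratio of reader SD to measured spread fell.

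Imaging the same subjects on the same day equalises the true spread but not the measured spread. Image error common to all readers counts as between-subject variance. Such error is plausible here, because the readers see the same images and start from one technologist's contour (Protocol 6.8.2). Percentage of error avoids the between-subject spread but divides by the mean reading, so it moves if contrast shifts measured values.

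At stake is the reading of four of the five secondary objectives. A change in either measure could be reported as a change in reader variability when the disagreement in points or mL has not changed.

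**Working it through.** **The plan's own figure.** The documents give no target, assumption or power for any inter-reader measure, so there is nothing on this point to reproduce. The one stated power, for the primary paired t-test (difference 2.75, SD 10, two-sided 0.05), does reproduce: 0.904 at 143 evaluable subjects against the stated 90%.

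**Notation.** W is the reader SD. B is the SD of everything the readers share: true values plus common image error. With no constant reader offset, ICC = B² / (B² + W²). For one subject, percentage of error = 100 × SD of the two readings / their mean.

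**1. LVEF and the ICC.** From the Protocol: a gain of 2.75 points in mean absolute error. Assumed: unbiased normal errors, mean absolute error 8.0 unenhanced and 5.25 enhanced, true LVEF SD 13, W = 5 unenhanced, no CMR error.

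- Total error SD = mean absolute error / 0.798, giving 10.03 and 6.58. The variances are 100.5 and 43.3.
- *Case A, the whole gain is shared error and W stays at 5.* Shared error variance is 100.5 − 25 = 75.5 unenhanced and 43.3 − 25 = 18.3 enhanced. ICC = (169 + 75.5) / (169 + 100.5) = 0.907 unenhanced and (169 + 18.3) / (169 + 43.3) = 0.882 enhanced. The ICC falls although the readers are unchanged.
- *Break-even in Case A.* With B² = 187.3 held, the ICCs are equal when W = √(187.3 × 25 / 244.5) = 4.38, a cut of 12.5%. Over unenhanced error 7 to 10, LVEF SD 12 to 15, W 3 to 5 and CMR error SD 0 to 3, the cut needed is 8.7% to 15.1%.
- *Case B, both error parts shrink in proportion.* W = 5 × 5.25 / 8 = 3.28 and W² = 10.8. ICC = (169 + 43.3 − 10.8) / (169 + 43.3) = 0.949. The ICC rises, correctly.

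**2. Volumes, both measures together.** All inputs are assumed. Unenhanced: mean 120 mL, B = 30, W = 15. Enhanced values 25% larger: mean 150 mL, B = 37.5, W still 15.

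- ICC: 900 / 1125 = 0.800, then 1406.25 / 1631.25 = 0.862.
- Percentage of error: the expected SD of two readings is 0.798 × 15 = 11.97 mL. At the mean volume this is 11.97 / 120 = 10.0%, then 11.97 / 150 = 8.0%. In simulation the median over subjects goes from 8.6% to 6.9%, the same one-fifth drop.
- Both measures improve with identical mL disagreement.
- If W also grows by 25%, to 18.75 mL, the ICC stays at 1406.25 / (1406.25 + 351.6) = 0.800 and percentage of error does not move.

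**3. Volumes, the other direction.** Assumed: true SD 40 mL, scale 0.95 in both modalities, W = 15 in both, shared image error SD 25 unenhanced and 10 enhanced. The simulated ICC goes from 0.901 to 0.872.

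**4. Percentage of error for LVEF.** With W = 5 and mean 42, the simulated median is about 8.1% to 8.2% for B from 10 to 14, so it does not react to spread. At mean 46 and B = 10 it is 7.5%, so it does react to the mean.

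**The case against.** **Percentage of error is planned as well.** This stands. A reader of the synopsis might infer that the ICC is the only yardstick, but Protocol 8.3.1.2 to 8.3.1.5 and SAP 8.2.2 to 8.2.5 add a measure that does not use between-subject spread. In Case A, with an assumed mean LVEF of 41, its simulated mean is 11.7% unenhanced and 11.3% enhanced, so the planned table would not show a worsening alone. It is only a partial answer, because it is scaled by the mean and for volumes can err in the same direction as the ICC.

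**The comparison is descriptive.** This stands. There is no test or threshold, and SAP 8.2.2 prints each ICC with a CI. In a simulation of Case A with 143 subjects the ICC shift is −0.024 (95% range −0.063 to +0.014), within the noise of one reader pair. Still, these figures are the only planned evidence for four objectives worded as demonstrations.

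**The ICC need not mislead when contrast works.** This stands. A reader might infer that the ICC goes wrong precisely when the primary objective is true. That requires nearly all the gain to be shared error. Protocol 1.1 blames poor border discrimination for poor reproducibility as well as poor accuracy, which fits Case B equally well. Removing a constant bias would leave B unchanged.

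**Relative disagreement is a legitimate choice.** This stands in part. If reader error grows with volume, a relative measure is reasonable. The plan does not say that this is what it means by variability.

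**Enrolment spread.** A reader might also infer that enrolling for an "approximately even distribution within four pre-defined LVEF groups" distorts the comparison. It does not follow: both modalities image the same subjects, so the true spread is common to both.

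**Conclusion.** The point holds in limited form. Neither planned measure isolates reader disagreement in LVEF points or mL, and a difference in ICC alone is not evidence that reader variability changed. The size is illustrative: an ICC of 0.907 unenhanced becomes 0.882 or 0.949 enhanced, depending on how the same accuracy gain divides between shared and reader error. Only the 2.75-point gain comes from the Protocol; every other input, and every volume input, is an assumption. The documents therefore fix neither the direction nor the size of any actual distortion, and they do not support saying that these objectives will get the wrong answer. The primary endpoint, its success rule and the sample size are untouched. This is a cheap improvement to a descriptive secondary analysis.

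**What to change.** In Protocol 8.3.1.2 to 8.3.1.5 and SAP 8.2.2 to 8.2.5:

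1. Add, for each reader pair and modality, the within-subject between-reader SD in LVEF points and in mL. Compute it as the root mean square of the per-subject SD between the two readers, √(Σd² / 2n), where d is the reader difference and n the number of subjects.
2. Report the enhanced/unenhanced ratio of this SD in the same subjects, with a 95% CI that respects the pairing.
3. Base the statement about a reduction on this figure. Keep the ICC, printed with that modality's between-subject SD, and the percentage of error as supporting measures. State that an ICC difference alone is not evidence of a change in reader variability.
4. Align the synopsis with Protocol 8.3.1.2.

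The root mean square form matters. The SD of paired differences divided by √2 would drop a constant offset between readers. With reader SD 3 and one reader 6 points higher throughout, it gives 3.0, while the root mean square gives √(9 + 36/2) = 5.2.

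Cost: wording changes and one more line per existing table. The per-subject SD is already the numerator of the percentage of error, so no new reads or data are needed. The downside is that the ICC is no longer the lead measure.
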